6.1.1. Retesting

If in the Investigator's judgement, the screening laboratory abnormalities are likely to be transient, then laboratory tests may be repeated. The Investigator's rationale should be documented. Laboratory values can be retested once during Screening after consultation with the Medical Monitor, provided that the patient can be evaluated for eligibility within the Screening period.

6.1.2. Rescreening

A patient who does not meet all study eligibility criteria may be allowed to return for rescreening after consultation with the Medical Monitor. The patient or legal guardian (if applicable) will be re-consented, and assent obtained (if applicable) if rescreening occurs outside of the 120-day screening window. If patients require rescreening, screening assessments previously obtained within 120 days prior to Day 1 may be used. In addition, X-rays, bone scans, ophthalmologic

examinations, exploratory DNA assessments, and blood and urine samples for exploratory analyses obtained within 120 days of Day 1 do not need to be repeated. Echocardiogram and ECG will be repeated if obtained 60 or more days prior to Day 1.

6.2. Efficacy Assessments

The efficacy of lumasiran will be assessed in all patients in both cohorts by evaluating changes in plasma oxalate levels; and plasma oxalate profile assessment in Cohort B only (Section 6.2.1); urinary oxalate (in non-anuric patients, Section 6.2.2), and measures of systemic oxalosis (Section 6.2.3).

In Cohort A patients, all blood and urine samples will be collected predose, when applicable. In Cohort B patients with a dialysis session on the day of dosing, samples will be collected prior to the dialysis session.

The efficacy of lumasiran on renal function will be assessed by eGFR (Section 6.3.4).

Change in the frequency and mode of dialysis will be assessed (Section 6.5.5.5).

In both cohorts, change in levels of urinary and plasma glycolate will be assessed.

6.2.1. Plasma Oxalate

Plasma oxalate levels will be assessed from blood samples collected in all patients; levels will be measured via central laboratory using a validated assay. The collection timing during Screening is detailed by cohort in Figure 1. During the treatment period, samples will be collected as specified in the Schedules of Assessments (see Table 1, Table 2, Table 3, and Table 4) and in Table 6.

6.2.1.1. Cohort A

In Cohort A patients, plasma oxalate levels will be assessed via blood samples collected throughout the study as specified in the Schedules of Assessments (see Table 1, Table 2, Table 3, and Table 4). The three most recent screening plasma oxalate samples collected prior to Day 1 will be used to assess eligibility; see Section 6.1 and Figure 1.

6.2.1.2. Cohort B

Plasma Oxalate Level

In Cohort B patients, plasma oxalate levels will be assessed via pre-dialysis blood samples collected throughout the study as specified in the Schedules of Assessments. From Screening to Day 1, at least 4 pre-dialysis blood samples obtained at least 7 days apart over the span of at least 28 days will be collected to assess eligibility. Up to 2 of the blood samples may originate from the pre-dialysis samples collected at the beginning of the plasma oxalate profile assessments performed during Screening (described below). See Figure 1.

Plasma Oxalate Profile

Plasma oxalate profiles will be performed as specified in the Schedules of Assessments to permit calculation of the AUC between dialysis sessions. The plasma oxalate profile assessment consists of an overnight visit requiring collection of up to 8 blood samples for plasma oxalate over the course of a 24-hour span, dependent on blood volume limitations and study center

facilities; blood sample collection schedule is described in Table 6, which includes collections before, during, and after the dialysis session. During Screening, there will be 2 separate profile assessments performed at least 7 days apart. See Figure 1.

During Screening, the blood sample timepoints described in Table 6 are relative to when dialysis is performed. During the treatment period, the timepoints described in Table 6 are relative to dialysis or when the dose is administered, as specified. The 24-hour postdose sample will be collected prior to beginning the next hemodialysis session, or 24 hours (± 3 hours) postdose if there is no hemodialysis session on the day following dosing.

In patients with ≥ 1 systemic oxalosis manifestation during the study, additional plasma oxalate profile assessments will be performed at the Month 36 and Month 48 visits, and blood sample collection timepoints are the same as described above.

6.2.2. Urinary Oxalate

In patients in both Cohort A and Cohort B who are not anuric (ie, patients who are able to continue to produce urine ≥ 100 ml per day) and are able to complete the collection procedure, 24-hour urinary oxalate excretion will be assessed. Since not all patients will be able to provide 24-hour urine samples, single-void urine samples (in triplicate) will be collected throughout the study in all patients who are not anuric. Table 12 shows the 24-hour urine collection procedure by study visit.

In patients who are able to comply with 24-hour urine collection procedures, urinary oxalate excretion will be determined from 24-hour urine sample collections to be completed at the time points specified in the Schedules of Assessment (see Table 1, Table 2, Table 3, and Table 4). Urinary oxalate concentrations will be analyzed centrally using a validated assay. 24-hour urine collections in patients not undergoing dialysis must meet pre-specified validity criteria (see Section 6.2.2.1).

For patients who are able to comply with the 24-hour urine collection procedure, three 24-hour urine collections will be scheduled during screening to establish baseline urinary oxalate excretion. For Month 6, three 24-hour urine collections will be scheduled within 14 days prior to dose to evaluate changes in oxalate concentrations over the 6-month interval. A single 24-hour collection will be scheduled at Month 3, Month 12, and then every 6 months thereafter as specified in the Schedules of Assessments (see Table 1, Table 2, Table 3, and Table 4). In patients undergoing dialysis, the timing of the collections relative to patients' weekly dialysis schedule should remain consistent for each patient, when possible.

Patients able to comply with 24-hour urine collections will either bring a 24-hour urine collection to the clinic, courier samples to the laboratory, or have their 24-hour urine collected during an inpatient stay at the time of the study visit.

All patients who are not anuric will have 3 single-void urine samples collected during Screening (first morning voids are preferred, when feasible). Following screening, single-void collections are performed within 7 days predose, as specified in the Schedules of Assessment (see Table 1, Table 2, Table 3, and Table 4). Samples may be collected as an outpatient prior to the visit or collected during the study visit prior to dosing, as applicable.

Table 12: 24-hour Urine Collection Procedure by Study Visit for Patients who are not Anuric

Study Visit and 24-hour Urine Collection Window	Number of 24-hour Collections	Notes
Screening (within 120-day period prior to initial dosing)	3 voided collections	Supervised 24-hour collections are encouraged unless patient/caregiver already familiar with collection procedure.
Month 6 (within 14 days prior to dosing)	3 voided collections	Supervised 24-hour collections are encouraged unless patient/caregiver already familiar with collection procedure.
Months 3, 12, and every 6 months through end of study	1 voided collection	--

6.2.2.1. Validity Criteria for 24-hour Urine Collections

Detailed instructions on 24-hour urine collections will be provided to patients or caregivers. A urine collection will be considered valid if each of the following criteria are met:

- The collection is between 18-26 hours in duration between the initial discarded void and the last void or attempt to void.
- No voids are missed between the start and end time of the collection.
- In patients not undergoing dialysis, the 24-hour creatinine content is at least 5 mg/kg for patients <6 years of age, and 10 mg/kg for patients \geq 6 years of age, as assessed by the study central laboratory.

In patients undergoing dialysis, 24-hour collections are not required to have a minimum creatinine content to be considered valid.

6.2.3. Measures of Systemic Oxalosis

As measures of the PD effect of lumasiran on systemic oxalosis, cardiac, dermatologic, skeletal, and ocular measures of oxalosis will be assessed in all patients where feasible according to age and where local IRB/IEC permits.

6.2.3.1. Cardiac

To assess the effect of lumasiran on cardiac outcomes driven by systemic oxalosis, echocardiograms will be performed; echocardiogram acquisition time will be standardized relative to dialysis session when applicable. Parameters to be followed include features of infiltrative cardiomyopathy including cardiac structure and function. Echocardiogram acquisition will be standardized and detailed in the study manual. Echocardiograms will be read centrally.

In addition to safety assessments described in Section 6.5.4, as a measure of systemic oxalosis, ECGs will be monitored to identify conduction disorders if normal at baseline or change in conduction disorders if present at baseline.

TriPLICATE 12-lead ECGs will be collected using standardized machines at the timepoints specified in the Schedules of Assessment (see Table 1, Table 2, Table 3, and Table 4). During periods of time when the COVID-19 pandemic impedes the ability of patients to travel to the study site, ECG assessments may be completed up to 2 months after the Month 3 timepoint, up to 5 months after the Month 6 timepoint, and up to 11 months after the Month 12 timepoint. 12-lead ECGs will be centrally read.

6.2.3.2. Dermatologic

In cases where skin manifestations due to systemic oxalosis are reported during the course of the study, (eg, patient presenting with skin lesion during physical examination) photographs of the lesions should be obtained. The Investigator may engage a local dermatologist's opinion if required. When a skin manifestation of systemic oxalosis is observed, at each succeeding visit, photographs of the affected area will continue to be collected to record the resolution or worsening of the manifestation. Further details will be provided in the study manual.

6.2.3.3. Skeletal

Radiographs (X-rays) of hands, hip, knee, and chest will be obtained and read centrally for features of skeletal oxalosis, where local IRB/IEC permits at the timepoints specified in the Schedules of Assessment (see Table 1, Table 2, Table 3, and Table 4), where feasible based on patient compliance. During periods of time when the COVID-19 pandemic impedes the ability of patients to travel to the study site, X-rays may be completed up to 1 month after Day 1, and up to 11 months after the Month 12 timepoint.

Only a subset of these x-rays will be collected at selected study centers. In addition, a reading of bone age will be performed for patients who have not yet reached skeletal maturity. Results will be interpreted using a scale developed in conjunction with the central reading core laboratory, as detailed in the study manual.

Optional bone scans will be performed in only Cohort B patients ≥ 18 years of age to assess calcium oxalate systemic deposition, where local IRB/EC permits and if patient consents to the bone scan. During periods of time when the COVID-19 pandemic impedes the ability of patients to travel to the study site, optional bone scans may be completed up to 1 month after Day 1, and up to 11 months after the Month 12 timepoint.

6.2.3.4. Ocular

Ophthalmology

The following ophthalmologic exams will be performed: Color Fundus Photography (CFP), Optical Coherence Tomography (OCT), and, where available at select sites, Fundus Autofluorescence (FAF).

Ophthalmologic exams with fundus photography will be standardized and the fundus photographs will be read centrally. OCT assessments will also be standardized and read centrally. For young children unable to cooperate, examinations will be optional. Anesthesia

will not be used in any of these ocular assessments. Results from any clinically obtained exams performed as standard of care may be collected.

During periods of time when the COVID-19 pandemic impedes the ability of patients to travel to the study site, ophthalmologic exams may be completed up to 1 month after Day 1, and up to 11 months after the Month 12 timepoint.

Best Corrected Visual Acuity (BCVA)

Where available, BCVA using Early Treatment Diabetic Retinopathy Study (ETDRS) charts will be assessed longitudinally throughout the course of the study to evaluate for changes which correspond to changes in retinal oxalate deposition. Exams will be standardized across applicable sites. In younger patients <6 years of age, alternate visual acuity testing per local standard practice may be performed (eg, LEA symbols). In sites where ETDRS testing is not available, Snellen or LEA symbol charts may be used for BCVA. Testing is not required in preverbal infants.

6.3. Renal Assessments and Additional Pharmacodynamic Measurements

Renal assessments and additional pharmacodynamic assessments include: nephrocalcinosis as assessed by renal ultrasound (Section 6.3.1); frequency of renal stone events (Section 6.3.2); urine oxalate:creatinine ratio (in available urine collections; Section 6.3.3); and eGFR (Section 6.3.4).

Glycolate concentrations may be collected at the same time as the plasma oxalate sample collection (Section 6.2.1) as specified for Screening (Figure 1) and as per the Schedules of Assessments (see Table 1, Table 2, Table 3, and Table 4). Additional collections may be performed at the discretion of the Investigator.

In Cohort A patients, all samples will be collected predose, when applicable. In Cohort B patients with a dialysis session on the day of dosing, samples will be collected prior to the dialysis session.

All PD assessments will be analyzed centrally. Details regarding the processing and aliquoting of samples for storage and analyses will be provided in the Laboratory Manual.

Where local regulations allow, and infrastructure is in place, home nursing may be used to collect urine and blood samples.

6.3.1. Renal Ultrasound

Renal ultrasounds will be obtained locally, as specified in the Schedules of Assessment (see Table 1, Table 2, Table 3, and Table 4) when feasible; anephric patients are exempt from renal ultrasound assessments. Renal ultrasound will be performed according to instructions provided in the Study Manual in a standardized manner. Renal ultrasounds will be reviewed centrally.

During periods of time when the COVID-19 pandemic impedes the ability of patients to travel to the study site, renal ultrasounds may be completed up to 1 month after Day 1, up to 5 months after the intended timepoint for assessments scheduled prior to Month 12, and up to 11 months after the intended timepoint for visits at Month 12 and subsequent timepoints, if necessary.

6.3.2. Renal Stone Events

A renal stone event is defined as an event which includes at least one of the following:

- Visit to healthcare provider (eg, outpatient clinic, urgent care, emergency department, procedure) because of a renal stone
- Medication for renal colic
- Stone passage
- Macroscopic hematuria due to a renal stone

All relevant clinical information pertaining to the event should be obtained, including laboratory values, medical records, discharge summaries, and medical test results.

Since renal stone events are recorded as an efficacy assessment for lumasiran, these will not be treated as AEs or SAEs. However, if a patient experiences other AEs or SAEs during a renal stone event, they should be reported (see Section 6.5.6.1).

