
Primary
 
Cohort A
 
Evaluate the effect of lumasiran on plasma oxalate in patients who are not on dialysis therapy 
Cohort B
 
Evaluate the effect of lumasiran on plasma oxalate levels in patients who are on dialysis therapy	
Cohort A
 
Percent change in plasma oxalate from Baseline to Month 6 
Cohort B
 
Percent change in pre-dialysis plasma oxalate from Baseline to Month 6

Secondary
 
Evaluate the effect of lumasiran on change in plasma oxalate area under the curve (AUC) between dialysis sessionsEvaluate the long-term effects of lumasiran on change in plasma oxalateEvaluate the effect of lumasiran on change in urinary oxalate excretionEvaluate quality of life in patients with PH1Characterize the PK of lumasiranEvaluate the effect of lumasiran on nephrocalcinosisEvaluate the effect of lumasiran on dialysis requirements	
Primary Analysis Period (Baseline to 6 months)
 
Percent change in plasma oxalate AUC between dialysis sessionsAbsolute change in plasma oxalateChange in the following parameters:
Urinary oxalate

Objectives	Endpoints

 • Evaluate the effect of lumasiran on the occurrence of renal stones • Evaluate the effect of lumasiran on renal function • Evaluate the effect of lumasiran on change in measures of systemic oxalosis 	
 ○ QoL assessed by the PedsQL Total Score for patients ≥ 2 to <18 years of age at consent, and as assessed by KDQOL Burden of Kidney Disease and Effect of Kidney Disease on Daily Life subscales, and SF-12 Physical Component Summary and Mental Component Summary, in patients ≥ 18 years at consent • Plasma PK parameters of lumasiran

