Bone scan (Optional)	Only in adult Cohort B pts Section 6.2.3	X								
Renal stone events	Section 6.3.2									Continuous
Review/record AEs	Section 6.5.6.2									Continuous
Prior and concomitant medications	Section 5.3									Continuous

Abbreviations: ADA=antidrug antibody; AE=adverse event; AGXT=alanine-glyoxylate aminotransferase gene; D=day; DNA=deoxyribonucleic acid; ECG=electrocardiogram; hrs=hours; LFTs=liver function tests; M=Month; Opt=optional; PD=pharmacodynamic; PE=physical examination; PH1=primary hyperoxaluria type 1; PK=pharmacokinetic; POx=plasma oxalate; pts=patients; SAE=serious adverse event; wk=week; y=year(s)

* During periods of time when the COVID-19 pandemic impedes the ability of patients to travel to the study site, the visit window is expanded to ±14 days after Week 2.

Notes:

- One month is defined as 28 days.
- Only SAEs are collected in the Screening period. Starting on D1, all AEs (including SAEs) are collected.
- Assessments are to be performed prior to dosing, where applicable. When scheduled at the same time points and where feasible, the assessments of vital signs and 12-lead ECGs should be performed before physical examinations and blood sample collections.
- Visits and study drug dosing may be conducted offsite where applicable country and local regulations and infrastructure allow (at the discretion of the Investigator, based on safety and tolerability), provided the patient has tolerated a dose of lumasiran administered in the clinic. If a visit is conducted offsite, a body system assessment may be performed in lieu of a physical examination.
- In situations where a study visit is unable to be completed (either at the site or offsite by a healthcare professional), the Investigator (or delegate) will verbally contact the patient within the study visit window to assess concomitant medications, renal stone events, adverse events, and healthcare utilization.
- Patients who discontinue from study drug prior to completion of the Month 6 assessments should be encouraged to remain on the study and complete assessments (including 24-hour urine collections but excluding PK assessments) through Month 6. They will also be asked to complete safety follow-up visits once every 3 months, per the safety follow-up schedule (see Table 3 or Table 4), for up to 12 months after the last dose of lumasiran (Section 3.3.1). See Section 4.3.1 for instructions for patients who discontinue study drug.

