6.5.6. Adverse Events

6.5.6.1. Definitions

Adverse Event

According to the ICH E2A guideline Definitions and Standards for Expedited Reporting, and 21 CFR 312.32, IND Safety Reporting, an AE is any untoward medical occurrence in a patient or clinical investigational subject administered a medicinal product and which does not necessarily have a causal relationship with this treatment.

Renal stone events (as defined in Section 6.3.2) are recorded for efficacy assessment of lumasiran. These events will not be treated as AEs or SAEs. Other AEs or SAEs occurring during a renal stone event are reported.

Serious Adverse Event

An SAE is any untoward medical occurrence that at any dose:

- Results in death
- Is life-threatening (an event which places the patient at immediate risk of death from the event as it occurred. It does not include an event that had it occurred in a more severe form might have caused death)
- Requires inpatient hospitalization or prolongation of existing hospitalization
- Results in persistent or significant disability or incapacity
- Is a congenital anomaly or birth defect
- Is an important medical event that may not be immediately life-threatening or result in death or hospitalization but may jeopardize the patient and may require intervention to prevent one of the other outcomes listed in the definition above (eg, events include allergic bronchospasm requiring intensive treatment in an emergency room or at home, blood dyscrasias, convulsions, or the development of drug dependency or abuse).

Adverse Events of Clinical Interest

The following are considered to be AEs of clinical interest:

- Alanine aminotransferase (ALT) or aspartate aminotransferase (AST) $>3\times$ upper limit of normal (ULN)
- Severe or serious injection site reactions (ISRs); ISRs that are associated with a recall phenomenon (reaction at the site of a prior injection with subsequent injections), or those that lead to temporary dose interruption or permanent discontinuation of study drug.

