3.2. Secondary Endpoints

The following are the secondary endpoints in the Primary Analysis Period:

Primary Analysis Period (Baseline to 6 months)

- Percent change in plasma oxalate AUC between dialysis sessions (Cohort B)
- Absolute change in plasma oxalate
- Change in the following parameters:
 - Urinary oxalate, which is measured by percent and absolute change in 24-hour urinary oxalate excretion corrected for BSA and spot urinary oxalate:creatinine ratio, when available.
 - QoL assessed by the PedsQL Total Score for patients ≥ 2 to < 18 years of age at consent, and as assessed by KDQOL Burden of Kidney Disease and Effect of Kidney Disease on Daily Life subscales, and SF-12 Physical Component Summary and Mental Component Summary, in patients ≥ 18 years at consent
- Plasma PK parameters of lumasiran

The following are the secondary endpoints in the Long-term Extension Period:

Long-term Extension Period (6 months to end of study)

- Percent change in plasma oxalate AUC between dialysis sessions (Cohort B)
- Percent and absolute change in plasma oxalate
- Change in the following parameters:
 - Nephrocalcinosis as assessed by renal ultrasound
 - Frequency and mode of dialysis (Cohort B)
 - Frequency of renal stone events
 - Urinary oxalate, measured by 24-hour urinary oxalate excretion corrected for BSA, and spot urinary oxalate:creatinine ratio
 - Renal function as assessed by eGFR (Cohort A)
 - Measures of systemic oxalosis in the following systems:
 - Cardiac

- Dermatologic
- Skeletal
- Ocular
- QoL (quality of life) assessed by the PedsQL Total Score for patients ≥ 2 to < 18 years of age at consent, and as assessed by KDQOL Burden of Kidney Disease and Effect of Kidney Disease on Daily Life subscales, and SF-12 Physical Component Summary and Mental Component Summary, in patients ≥ 18 years at consent

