4. PATIENT POPULATION

4.1. Patient Definitions

The populations (analysis sets) are defined as follows:

- Safety Analysis Set: All patients who received any amount of lumasiran during study.
- Full Analysis Set: All patients who received any amount of lumasiran and have at least one evaluable plasma oxalate value (pre-dialysis in Cohort B) at baseline and at least one evaluable plasma oxalate value from assessment(s) at Month 3 through Month 6
- PK Analysis Set: All patients who received any amount of lumasiran, have at least 1 postdose blood sample for PK parameters, and have evaluable PK data.

The Safety Analysis Set will be used for safety analyses and the sensitivity analysis of efficacy. The Full Analysis Set will be used to evaluate efficacy endpoints. The PK Analysis Sets will be used to conduct PK analyses.

This study will consist of 2 periods: a 6-month Primary Analysis Period followed by a long-term (54 months) extension period. The Primary Analysis Period starts at the first date/time of lumasiran dose administration and ends at either the date/time of lumasiran dose administration at Month 6 (exception being that Month 6 assessments (eg, plasma oxalate and PK assessments) which occur after the Month 6 dose will be included) or the date of the Month 6 visit (Day 169) for patients who discontinued treatment prematurely. Primary analysis will be conducted using the Primary Analysis Period data collected through 6 months.

The Long-term Extension Period, starts at the date/time of lumasiran dose administration at Month 6 and is through the end of the study. Analysis of the Long-term Extension Period will focus on long-term efficacy and safety effects of lumasiran.

Patients who discontinue from study drug during the 6-month Primary Analysis Period (defined above) will be encouraged to remain on the study and complete assessments (including plasma oxalate but excluding PK assessments) through Month 6. They will also be asked to complete safety follow-up visits, once every 3 months, per the safety follow-up schedule for up to 12 months after the last dose of lumasiran.

Patients who discontinue study drug after Month 6 will be asked to return for their next scheduled visit to complete early termination (ET) assessments and complete safety follow-up visits, once every 3 months, per the safety follow-up schedule for up to 12 months after the last dose of lumasiran.

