5.2. General Methods

Continuous data will be described using descriptive statistics such as the number of observations (n), mean, standard deviation, standard error, median, quartiles, minimum, and maximum. For the summary statistics of all numerical variables unless otherwise specified, minimum and maximum will be displayed to the same level of precision as reported. Median and mean will be presented to the level of precision collected in the database plus one additional decimal. The standard deviation and standard error will be presented to the level of precision collected in the database plus 1 additional decimal. For any assessments with repeated collections at a given study visit (eg height) the mean will represent the value at that visit unless otherwise noted. For biomarker and/or lab data, if any value is recorded as <lower limit of detection (LLOD) then the value assigned for calculations will be the LLOD.

Categorical and ordinal data will be described using the patient count and percentages in each category. When count data are presented, the percentage will not be presented when the count is zero.

Summaries of tables and figures for each study period will include all data collected during the corresponding period as defined in Section 4.1.

The per-patient listings will include all data collected during each study period. For per-patient listings of the extension periods, there will be a variable to indicate the period of the data collection (Primary Analysis Period or Extension Period).

Day 1 will be defined as the day of the first dose of lumasiran. Study day is calculated relative to the first dose date of lumasiran for all patients:

If the assessment date is after the date of first lumasiran dose, then the study day will be calculated as:

$$\text{Study Day} = \text{Date of assessment} - \text{date of first dose of lumasiran} + 1,$$

If the assessment date is before the date of the first dose of lumasiran, then the study day will be calculated as:

$$\text{Study Day} = \text{Date of assessment} - \text{date of first dose of lumasiran}$$

Summary statistics will be presented, as well as 2-sided 95% confidence interval (CI)s for primary/secondary endpoints or selected parameters, as described in the sections below.

All data recorded on the CRF will be displayed in data listings.

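### Renal stone events are kept out of the AE/SAE tables as efficacy data, but the stone endpoint covers only the extension, so the visible SAP plans listings and no count or rate for Day 1 to Month 6

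*Protocol*

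**What the plan says.** **Safety side.** Protocol 6.3.2 takes renal stone events out of adverse event reporting and gives the reason: "Since renal stone events are recorded as an efficacy assessment for lumasiran, these will not be treated as AEs or SAEs". Protocol 6.5.6.1 repeats the exclusion and adds: "Other AEs or SAEs occurring during a renal stone event are reported". Neither section makes an exception for a stone event that itself leads to hospitalisation.

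**Efficacy side.** The objective in Protocol 2 has no time limit: "Evaluate the effect of lumasiran on the occurrence of renal stones". The matching endpoint, "Frequency of renal stone events", stands only in the Long-term Extension list in Protocol 2 and SAP 3.2. The Primary Analysis Period list covers plasma oxalate AUC, absolute plasma oxalate, urinary oxalate, quality of life and PK.

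**Periods.** SAP 4.1: "The Long-term Extension Period, starts at the date/time of lumasiran dose administration at Month 6". SAP 5.2: "Summaries of tables and figures for each study period will include all data collected during the corresponding period". SAP 5.8 sets a database lock once the last patient completes Month 6, and a separate Primary Analysis Period CSR follows from it.

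**Collection.** Protocol Table 1 marks stone events as continuous during the Primary Analysis Period. Its notes say that when a visit cannot be completed, the site contacts the patient "to assess concomitant medications, renal stone events, adverse events, and healthcare utilization".

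**The concern.** The reason for removing stone events from safety reporting is that they are counted as efficacy. In the visible plan, that reason is not met in the first six months, because no efficacy endpoint for that period counts them. An event in this window falls between the two sets of tables.

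Protocol 1.1 names an obstructive stone among the events that can lead to acute or chronic worsening. The Month 6 report would carry a baseline stone figure (SAP 6.2 includes the number of renal stone episodes) with no planned on-treatment figure beside it, so a change in either direction would have to be counted by hand from listings. If some stone events led to hospital admission, the SAE table could look better than the patients' full experience. With 20 patients, one patient whose only serious event was a stone admission represents 1/20 = 5 percentage points of the SAE proportion. In a cohort of 6, the planned minimum, it is 1/6 = 16.7 points.

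**Working it through.** The point rests on text. The plan states no figure to reproduce, and the sample size of 20 is based on feasibility.

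**Step 1. Trace a stone event at, say, Month 4.**

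| Possible place | Governing text | Is it counted there? |
|---|---|---|
| AE and SAE tables | Protocol 6.3.2, 6.5.6.1 | No; only other AEs/SAEs during the event |
| Special safety summaries | SAP 7.6.1 | No; injection site reactions and hepatic events only |
| Primary Analysis Period secondary endpoints | SAP 3.2, 7.3.1 to 7.3.3 | Not listed |
| Extension stone endpoint | SAP 3.2, 4.1; contents entry 7.3.4.5 | Period starts at the Month 6 dose; body of the section redacted |
| Exploratory analyses | SAP 7.4 | No stone item; resource use is summarised, not by cause |
| By-patient listings | SAP 5.2 | Yes |

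**Step 2. Look for signs that a Month 6 stone table was intended.** SAP 5.4 takes the 12-month history as a baseline, SAP 10.1 gives rules for annualising it, and SAP 5.5 gives an imputation rule for partial stone dates without limiting it to a period. The derivations are thus largely in place. SAP 8 records that a Month 6 cardiac oxalosis analysis was added to specify an analysis for the primary period (SAP 7.4.1). Cardiac oxalosis, like stones, was otherwise an extension-only endpoint. SAP 8 lists no similar addition for stones.

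**Step 3. Size of the window** (28-day months, as the protocol defines them).

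- Primary Analysis Period: 6 × 28 = 168 days.
- Whole study: 60 × 28 = 1,680 days.
- Share: 168 / 1,680 = 10%.
- Patient-years, assuming 20 patients with full follow-up: 20 × 168 / 365.25 = 9.2, against 20 × 1,680 / 365.25 = 92.0 for the whole study.
- One cohort of 6: 6 × 168 / 365.25 = 2.8 patient-years.

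**Step 4. What cannot be computed.** The number of affected events would be 9.2 times the on-treatment stone rate. The documents do not give that rate. It may also differ between the cohorts, since Cohort B is on hemodialysis and the protocol provides for anuric and anephric patients. No event count is therefore offered.

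**The case against.** **The section that defines the stone analysis is redacted.** This stands as a limit. SAP 7.3.4.5 survives only as a contents heading. Its text might use events from Day 1 or show them by period, so it cannot be said that no stone analysis of the first six months exists. But its heading sits under the Long-term Extension Period, and the places where a Month 6 table would belong (SAP 3.2, 7.3.1 to 7.3.3 and 7.6) are readable and contain none. The safety half of the point does not depend on redacted text.

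**SAP 5.2 is an inclusion rule, and SAP 5.8 brings all data entered by the lock into the Primary Analysis Period CSR.** Both are fair readings, and SAP 5.2 also requires listings of all CRF data. In a largely descriptive study of 20 patients, a listing is real reporting. Yet neither section defines a stone table, and a listing supplies no count, rate or denominator.

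**The safety reporting is not blind.** Accompanying AEs and SAEs reach the tables. All hospitalisations, urgent visits and procedures are collected (Protocol 6.10), and doctor and hospital visits are summarised (SAP 7.4.4). This stands, but those summaries do not separate stone-related care from other care.

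**Placing clinical outcomes after Month 6 is a consistent choice.** Nephrocalcinosis, eGFR and dialysis frequency are also extension-only endpoints. That is a reasonable design, but stone events are the ones that the protocol explicitly removes from AE reporting on efficacy grounds. eGFR, by comparison, still appears in the laboratory shift tables (SAP 7.6.3).

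**Conclusion.** The point holds in a limited form. On the readable text, stone events from Day 1 to Month 6 are planned for by-patient listings but for no efficacy or safety count or rate in the Primary Analysis Period CSR. The window is 10% of planned follow-up and the whole of the period that the first report covers.

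A reader might infer more, and the documents do not support it:

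- That these events go unreported. Listings are planned, and SAP 7.3.4.5 cannot be read.
- That stone-related admissions vanish. Other AEs/SAEs during the event are reported, and hospital use is captured without attribution to stones.
- That the AE profile is more favourable than the truth. It could look better; whether it does depends on events that the documents cannot predict.
- That the DMC does not see stone data. What it receives is set in a charter that is not among the documents.

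The conclusion assumes that the analyses follow the endpoint lists and period definitions as written. The 9.2 patient-years further assume 20 patients with full follow-up.

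**What to change.** In SAP 3.2 and 7.3, with a cross-reference in 7.6, add for the Primary Analysis Period, by cohort in the Safety Analysis Set:

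- the number and percentage of patients with at least one renal stone event;
- the number of events;
- events per patient-year from Day 1 to the end of the period, beside the baseline annual rate;
- the events that involved hospitalisation, identified from the stone-event and resource-use records and shown separately from SAEs.

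The Safety Analysis Set is preferable here because the Full Analysis Set requires an evaluable plasma oxalate value between Month 3 and Month 6, which has no bearing on whether a stone event occurred. The rates should stay descriptive: in a cohort of 6, one event moves the rate by 1 / 2.8, or about 0.36 per patient-year.

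Because the table would sit beside the baseline rate, the worked example in SAP 10.1 should be put right at the same time. It prints 2 × (8/12) = 3, but 2 × (8/12) = 1.33; the stated result of 3 comes from 2 × (12/8).

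Investigator reporting rules, sample size and the primary analysis do not change. Flagging recorded hospitalisation is enough, and no retrospective judgement of seriousness is needed. The cost is SAP wording and a little programming on data already collected. The downside is a safety picture that may look slightly less favourable.
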